### Allocation:

Participants are randomized using a centralized random number assignment for treatment allocation developed at OHSU and assigned through RedCap.

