## **Study Population**

### **a) Number of Subjects**

In Phase 1, potential participants will be pulled from a convenience sample at a Portland clinic providing care for the urban area. An initial target sample of 100 Hepatitis C positive participants will be enrolled for DBS validation. Power will be reassessed based on feedback from receiver operating curve model and additional participants enrolled up to a total of 100 Hepatitis C Positive participants, if necessary. A total of 500 potential participants can be screened expecting 1 in every 4 participants will be positive HCV.

In Phase 2, rural peer care coordinators (PCCs) and research assistants recruit up to 200 PWUD participants from high-needs rural Oregon counties. Study staff specifically target untreated populations recruited from local syringe exchange programs and direct community outreach (e.g. community barbeques, parks, homeless shelters, food pantries, etc.). Participants are encouraged to refer others for study screening.

A subset of up to 40 study participants will complete in-depth qualitative interviews regarding their experiences of hepatitis C treatment.

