**Setting**

**Participating Sites:**

1 Oregon Health & Science University (OHSU) leads the project, under the direction of [name]. OHSU will participate in data quality assurance during study implementation analysis, train PCCs and research assistants (RAs) in study procedures, conduct analyses, and disseminate qualitative and quantitative results. HIV Alliance and Comagine are deferring to OHSU’s IRB; the Oregon Health Authority will be using its own IRB for project review.

2 HIV Alliance is a community based service organization providing support for HIV and HCV treatment and prevention and syringe exchange services in rural Oregon counties. HIV Alliance outreach workers will serve as intervention PCCs. HIV Alliance PCCs will recruit and provide linkage to care for PWUD, and an HIV Alliance research assistant staff will support HIV Alliance syringe exchange staff in collecting survey and laboratory data.

3. Bay Area First Step (BAFS) is a community based service organization that provides housing, and peer-delivered services designed to support individuals and families. BAFS peer mentors will serve as intervention PSSs. BAFS PSSs will recruit and provide linkage to care for PWUD and collect survey data. BAFS plays an active role in the community and has strong relationships with potential participants.

4. Comagine conducts qualitative focus groups and interviews and lead the qualitative analysis.

5. Oregon Health Authority investigators will assist in administrative support of tele-HCV treatment and advise the study team on implementation, interpretation, and dissemination of study findings.

6. Implementation Locations: The study catchment area includes Douglas, rural Lane, Josephine, Coos, Curry, Tillamook, Umatilla, and Clatsop counties.

7. Central City Concern: CCC is a community-based homelessness services organization located in Portland, Oregon. They will participate as the Phase 1 site for DBS validation. CCC hepatitis C team staff will perform usual HCV screening and linkage-to-care interventions, consent individuals for DBS validation study inclusion, perform DBS testing, and deliver and track incentives.

8. Oregon Washington Health Network (OWHN) is a community-based network that addresses mental and physical health, and houses peer support specialists. Peer support specialists will recruit participants and facilitate telemedicine appointments. The OWHN research assistant will consent participants and conduct study assessments.

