#### Phase 2:

Participants are randomized to peer-facilitated telehealth-HCV treatment intervention versus referral to local HCV treatment providers to initiate HCV treatment. After labs confirm preliminary eligibility, randomization will be generated by REDCap after baseline and consent. Participants with a CTP of 6 will connect with a study clinician over WebX to confirm eligibility. The participant is withdrawn if the study clinician deems ineligible. Local HCV treatment referral providers have treated at least one patient with HCV previously. They are encouraged to participate in the OHSU HCV ECHO tele-mentoring sessions, but are not study participants.

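### Allocation and models leave out recruiting organisation: no bias results, but chance site imbalance is uncontrolled and some precision is lost

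*Combined protocol and SAP*

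**What the plan says.** The Allocation section consists of this sentence: "Participants are randomized using a centralized random number assignment for treatment allocation developed at OHSU and assigned through RedCap". The Phase 2 text under Intervention Design adds the timing ("randomization will be generated by REDCap after baseline and consent") and the two arms ("Participants are randomized to peer-facilitated telehealth-HCV treatment intervention versus referral to local HCV treatment providers to initiate HCV treatment"). No ratio, block structure or stratification factor is given in either place.

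Number of Subjects says that staff will "recruit up to 200 PWUD participants from high-needs rural Oregon counties". Participating Sites gives the area: "The study catchment area includes Douglas, rural Lane, Josephine, Coos, Curry, Tillamook, Umatilla, and Clatsop counties". It also describes three organisations that recruit for Phase 2, with different staffing:

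- HIV Alliance: "HIV Alliance PCCs will recruit and provide linkage to care for PWUD", with a research assistant supporting data collection.
- Bay Area First Step (BAFS): "BAFS PSSs will recruit and provide linkage to care for PWUD and collect survey data".
- Oregon Washington Health Network (OWHN): peers recruit, and a research assistant takes consent and does the assessments.

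On the control side, the requirement for referral providers is that "Local HCV treatment referral providers have treated at least one patient with HCV previously". Under Study Arm 2, the community provider also does the SVR12 laboratory test.

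Data Analysis specifies logistic regression for SVR12, initiation and completion, and mixed models for the Hypothesis 4 outcomes. The fixed effects of interest are time, arm and their interaction. A baseline variable enters as a covariate if its standardised mean difference (SMD) exceeds 0.25 and p is below .2. Demographics are the only example given. Organisation, site and county are not mentioned.

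**The concern.** The comparator is whatever treatment is available locally, and the control-arm SVR12 sample depends on a local provider. A missing viral load counts as non-suppressed in the main analysis. Local access and local follow-up therefore both feed into the primary outcome, and peer support is delivered by three differently staffed organisations. Site is a natural candidate for a prognostic factor.

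If nothing holds the arms balanced within site and the model has no site term, two things follow. In a given trial, one arm may by chance contain more participants from places where cure is easier to obtain, and the observed difference moves for a reason unrelated to telemedicine. Between-site variation also stays in the error term, so the test is somewhat less powerful than the same data would allow.

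**Working it through.** **Inputs.** From the documents: N up to 200, eight counties, three recruiting organisations. The documents give no Phase 2 power, alpha, effect size or SVR12 rates, so there is no stated figure to reproduce. Assumed throughout: 1:1 ratio, two-sided 5% test, and the site shares and SVR12 rates shown below. Simple randomisation is taken as the unfavourable case; the plan does not say that it is used.

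**Step 1: how uneven can sites become?** With equal counties, 200/8 = 25 each.

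- 17:8 or worse in one county: 2·P(X ≤ 8 | 25, 0.5) = 0.108. In at least one of eight: 1 − (1 − 0.108)^8 = 0.60.
- 16:9 or worse: 0.230 in one county, and 1 − (1 − 0.230)^8 = 0.88 in at least one.
- Overall 110:90 or worse: 2·P(X ≤ 90 | 200, 0.5) = 0.18. This costs almost nothing: 2 × 110 × 90/200 = 99 effective per arm instead of 100.

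Lopsided counties are likely, but these figures do not show how far the result moves.

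**Step 2: effect on the arm difference.** Let V be the between-site variance of SVR12. The SD of the shift from site mix is about √(4V/N). For three equal organisations with mean SVR12 of 40%, the standard error of the arm difference is √(4 × 0.40 × 0.60/200) = 0.069.

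| Assumed SVR12 | V | Share of outcome variance (V/0.24) | SD of shift | Shift beyond ±3 points (20,000 simulated trials) |
|---|---|---|---|---|
| 30/40/50% | (0.1² + 0 + 0.1²)/3 = 0.0067 | 2.8% | √(4 × 0.0067/200) = 1.2 points | 1% of trials |
| 20/40/60% | (0.2² + 0 + 0.2²)/3 = 0.0267 | 11% | √(4 × 0.0267/200) = 2.3 points | 20% of trials |

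The 6.9-point standard error already contains this variation. Removing it gives √(0.0693² − 0.0115²) = 6.8 points or √(0.0693² − 0.0231²) = 6.5 points.

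**Step 3: error rate and power.** Simulation of 4,000 trials per setting with N = 200, comparing simple allocation with permuted blocks of 4 within site. The unadjusted analysis is a two-proportion z test. The adjusted analysis is a site-stratified Mantel-Haenszel test, standing in for a model with a site term.

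With no true effect and simple allocation, the mean shift was 0.0 points and the unadjusted type I error was 4.6% to 5.4%. Power for an assumed 20-point effect was:

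| Assumed setting (control SVR12) | Simple, unadjusted | Simple, adjusted | Blocked, adjusted |
|---|---|---|---|
| 3 organisations at 60/20/20% of N (20/35/50%) | 82.5% | 85.0% | 84.9% |
| 3 organisations at 60/20/20% of N (10/35/60%) | 83.6% | 90.5% | 90.5% |
| 8 equal counties (15% to 50%) | 82.2% | 82.6% | 84.5% |
| 8 equal counties (5% to 75%) | 81.2% | 88.2% | 89.5% |

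The simulation standard error is about √(0.85 × 0.15/4000) = 0.6 points, so differences of a point or so are noise. In the organisation settings the whole gain comes from adjustment.

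Blocking within site cuts the SD of the shift from 1.6–1.7 to 0.2–0.3 points (moderate spreads) or from 2.8–3.3 to 0.4–0.6 points (extreme spreads). Blocking without adjustment made the test conservative, with type I error of 2.6% to 4.2%.

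**Step 4: the plan's covariate rule.** Under simple allocation, at least one site indicator exceeds an SMD of 0.25 in 18% to 19% of trials with three organisations and in about 47% with eight counties. The rule would often be triggered if site were among the variables checked.

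**The case against.** The strongest defence is that the plan already has a safeguard. If organisation were checked under the covariate rule, then in the 20/40/60% case the rule would fire in every trial with a shift above 5 points. It would cut uncorrected shifts above 3 points from 20% to 9% of trials. At 30/40/50% none would remain. This stands as partial mitigation. However, organisation is not named, the rule makes the primary model depend on the imbalance observed, and it gives no precision when the arms happen to be balanced.

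It is also fair that the shift is small beside a 7-point standard error, and that stratified blocks add little power once the model adjusts.

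A reader might infer more than the documents support:

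- **That allocation is unrestricted.** The text is silent, and a REDCap table may be blocked or stratified without the protocol saying so. The finding is that the method is not specified.
- **That treatment access is known to differ between counties.** Potential Benefits describes little access in the region as a whole, and no county or organisation figures are given. Difference is plausible but undocumented.
- **That the comparison is biased.** The mean shift is zero and the type I error stays near 5%.
- **That stratifying would eliminate the problem.** Incomplete blocks leave some imbalance. Strata by organisation also do not balance counties: Recruitment Methods places HIV Alliance's existing work in four counties (Douglas, Lane, Josephine and Coos).

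**Conclusion.** The point holds as a gap in specification and a missed gain in efficiency, and no further. The plan states no ratio, blocking or strata and has no site term, although the design makes site a plausible prognostic factor.

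Under the assumed spreads, chance site mix adds a shift with an SD of about 1 to 2 points to an estimate whose standard error is about 7 points. Prespecified adjustment for organisation raises simulated power from 82.5–83.6% to 85.0–90.5%. These sizes rest on assumed SVR12 rates, organisation shares, a 1:1 ratio, simple allocation and a 20-point effect. If SVR12 hardly differs between organisations, the gain is close to nil. Validity of the primary test is not in question. Severity is minor to moderate.

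**What to change.** 1. **Data Analysis.** Name recruiting organisation (HIV Alliance, BAFS, OWHN) as a fixed factor in the models for Hypotheses 1 to 4, whatever imbalance is observed. This brings most of the gain, uses data already held, and remains possible before outcome analysis even if enrolment has begun. The SMD rule can stay for other variables.
2. **Allocation.** State the ratio and whether assignment is simple, blocked or stratified. If it can still be set, stratify the REDCap table by recruiting organisation, with centrally concealed blocks of randomly varying size. Say that this limits imbalance between organisations and does not control counties within them. Eight county strata would average only 25 participants each.

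The cost is two extra model terms for three organisations, one allocation table and no extra participants. There are two downsides. The odds ratio becomes conditional on organisation, which the report should say. In a non-blinded trial, site staff could also anticipate assignments if block sizes were fixed or known.

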### Intervention Design:

Central City Concern ONLY: Phase 1: Once in-house potential participants are identified they will be offered participation in the DBS study by IRB-trained CCC HCV team staff. Participants will provide a phlebotomy-derived blood sample and finger stick capillary blood sample for DBS card. These will be sent to MTL for DBS validation using standard human biohazard sample laboratory storage and shipping techniques consistent with MTL procedures. Incentives will be dispensed at the time of DBS sample collection or along with critical medications or services already provided, whichever method entails less on campus time for participants.

#### Phase 2:

Participants are randomized to peer-facilitated telehealth-HCV treatment intervention versus referral to local HCV treatment providers to initiate HCV treatment. After labs confirm preliminary eligibility, randomization will be generated by REDCap after baseline and consent. Participants with a CTP of 6 will connect with a study clinician over WebX to confirm eligibility. The participant is withdrawn if the study clinician deems ineligible. Local HCV treatment referral providers have treated at least one patient with HCV previously. They are encouraged to participate in the OHSU HCV ECHO tele-mentoring sessions, but are not study participants.

### Study Arm 1: Tele-HCV Treatment Arm Procedures:

Participants allocated to telemedicine intervention arm are scheduled for treatment assessment by a study clinician. For a majority of participants, this will also be the treatment initiation visit. If additional studies are necessary for routine treatment decision making, peers will assist participants in navigating health system barriers and arrangement of second telemedicine visit. The telemedicine study clinician will perform a standard of care hepatitis C treatment initiation history and submit a prescription for DAAs. Prior authorizations will be completed by study clinician pharmacist.

All patients initiating treatment will be prescribed HCV medication treatment for 4 weeks at a time. The majority of patients will require two separate dispensations at week 0 and week 4 for a total of 8 weeks of medications, with a small subset requiring third, 4-week dispensation for a total of 12 weeks of therapy. The study clinical pharmacist will check in with the participant by telephone or telemedicine visit at week 0, week 4, and end of treatment to 1) determine general medication tolerance, 2) assess quality of adherence and 3) dispense medications by mail or ensure medications received, depending on participant's insurance. Peers will assist participants in keeping telehealth appointments and navigating medication pick up or storage, if not mailed directly to the home. Participants who report new onset of jaundice or other signs of hepatic decompensation during participation will be scheduled for a follow up telemedicine visit with a physician by the research assistant, receive repeat laboratory studies if needed, and if necessary, be referred to local providers for ongoing medical care. If problems or side effects arise during treatment, participants will call the research assistant, who will connect them to a study clinician.

HCV labs will be repeated at 12 weeks post end of treatment and results will be relayed to the participant in the SVR12 follow up visit with the research assistant, along with follow up surveys. Those successfully achieving SVR12 will be counseled on ongoing harm reduction methods. Those showing persistent HCV viremia at 12 weeks post treatment will be referred to community-based HCV treatment providers for treatment re-initiation. All will be scheduled for 36 week post end of treatment survey visit.

SVR12 labs will be collected 12 weeks post-treatment in community partner labs. Dried Blood Spot specimens will be once again collected at this point by research assistants at the point of SVR12 survey data collection.

Telehealth visits will be performed via the chosen web platform of the participant. This includes but is not limited to: Facebook, Facetime, Skype, Zoom, Webex, WeChat, etc. The treatment initiation visit, pharmacist adherence assessments, and SVR12 lab communication will all be documented in the electronic medical record using PHI and no study identifiers.

#### Study Arm 2: Community Linkage-To Care Arm (Control Condition) Procedures:

Participants allocated to the community linkage-to-care arm will complete screening, be offered enrollment, and undergo informed consent as in the telemedicine arm. Following study inclusion and enrollment, research staff will refer the participant to a local community health clinic to engage in hepatitis C care and seek treatment. Peers will assist patients to engage with local primary care and health plan resources and will receive an information sheet on optional clinics to attend and questions to ask their provider. TAU participants will be encouraged to take this to their visit. Research assistants will outreach to participants regularly to determine if they have engaged in local health resources and schedule assessment visits. A bidirectional release of information will be requested. The study clinical pharmacist or research assistant will assess adherence medication adherence at week 4 and end of treatment via telephone. SVR12 laboratory testing will be performed by the community provider with at least one telephone reminder prior to lab due date. 12 weeks post end of treatment study assessments will coincide with SVR12 lab results visit and 36 week post end of treatment assessments performed as in the telemedicine arm.

Chart abstraction for participants in both arms will be performed in order to assess the number of and types of interactions the peers have with participants.

In either arm, participants who do not initiate treatment by 12 weeks after randomization will begin their assessment timeline, mirroring treatment timeline for an 8-week direct acting antiviral regimen. For these participants, the study research assistant will collect study assessments at week 16 (corresponding to 4-week post-treatment initiation), week 20-22 (corresponding to end of treatment visit), week 32 (corresponding to 12 weeks post-treatment visit), and week 56 (corresponding to 36

weeks post-treatment visit) after randomization; the primary study outcome will be assessed at 32 weeks after randomization.

Participant Assessments:

Phase 1:

- Blood draw and DBS specimen collection for HCV RNA and Hepatitis B core antibody

Phase 2:

Assessment/Activity	Pre-Screen	Screen	Baseline (Week 0)	4-Week after treatment initiation	End of Treatment	12-week Post-Treatment	***36-Week Post Treatment Completion	As Needed
Pre-Screening Survey	X							
Demographics		X						
Inclusion/Exclusion		X						
Rapid HCV Test	X							
CPT Assessment		X						
Participant Survey								
Medical Care History			X		X	X	***X	
Barriers to treatment			X		X	x	***X	
Engagement with Harm Reduction & Substance Use Treatment			X	X	X	X	***X	
Substance Use			X	X	X	X	***X	
Perceived Stigma of Drug Use			X	X	X	X	***X	
HCV Treatment History			X		X			
HCV Treatment Completion					X			
HCV Treatment Adherence				X	X			
Treatment Satisfaction					X			
Experience with Telemedicine					**X			
Experience with Peer Support Specialist					**X			
Blood Draw/ Medical Procedures								
HCV RNA		X				X		
Hepatitis B Sag		X						
Hepatitis B SAg		X						
Hepatitis B cAb		X						
Hepatitis A Ab		X						
CMP		X				X		

CBC		X				X	
INR/prothrombin		X					
HCV genotype		X					
B-HCG (women<50)		X					
SC Reviews Labs		X				X	
Ultrasound							**X
Telemedicine Visit			**X				
Medication Counseling			**X	**X	X*		
HCV Genotype and Resistance Testing							**X
Chart Abstraction					X	X	
Peer interaction log					X		
HCV treatment provider visits					X		
Administrative							
Written informed consent		X					
Locator Form	X		X	X	X	X	X
Master Enrollment Log			X				
Progress Note Check List	X	X	X	X	X	X	X
Reportable Events Log							X
Adverse Event							X
Inventory Form							X
Visit Compensation Log	X		X	X	X	X	X

\*\*\*X: 36 Week Survey only if participant qualifies

\*\*X: Only Telemedicine Pt.

\*X: Number of weeks of treatment depends on ppt.

Participants complete brief REDCap surveys regarding symptoms, substance use, and harm reduction engagement at baseline, 4 weeks, end of treatment, 12 post end of treatment, and 36 weeks post end of treatment. These surveys will be conducted over the phone or in person.

Participants undergo phlebotomy at screening and 12 post end of treatment.

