#### **Study Measures:**

The primary outcome is sustained viral response at 12 weeks post treatment (SVR12). Secondary outcomes include a) HCV treatment initiation, b) HCV Treatment completion (filled final prescription and self-reported > 90% HCV treatment pills taken), c) engagement with harm reduction resources, d) substance use, e) perceived stigma, and f) engagement in addiction treatment resources. Exploratory endpoints include a) treatment satisfaction with hepatitis C treatment, adapted from the single-item Medication Satisfaction Questionnaire, and b) reinfection vs. virologic relapse/failure.

Adherence to Phone Visits: Adherence to these phone visits is defined as +/- 5 days

Prescreen, baseline and follow-up surveys collected in the field or via phone will first be documented on paper forms. These will then be entered into REDCap by the RA. The source documents will be kept in a locked file cabinet in a secure location.

Qualitative interviews will be recorded on an encrypted recorder and stored on a secure, encrypted computer.

Survey data will be used to determine HCV status of participants with a detectable plasma HCV RNA, which were collected on or after SVR12 timepoint (either 12 weeks after end of treatment for those who initiated treatment or 32 weeks after randomization for those who did not initiate treatment). The primary SVR12 outcome will be sustained viral response 12 weeks after treatment for participants who initiated treatment within 6 months. Participants who did not start treatment within 6 months will be considered treatment failure. Measuring detectable plasma HCV RNA for both participants who initiated and did not initiate within 6 months of randomization will provide a framework to assess for potential biasing impact of spontaneous clearance on assumption of treatment failure for participants who did not initiate treatment within 6 months.

**Probable Relapse/Failure:** Probable virologic relapse or failure is defined as a detectable plasma HCV RNA 12 weeks or more after the end of treatment if a) participant denies any injection drug use, or b) participant injecting drugs but notes 100% adherence to recommendations on Safe injection practices, including use of clean works (cooker, cotton, rinse) with every injection.

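### The SVR12 test is obtained by a different route in each arm, with no back-up draw written down, and a missing result counts as failure in the main analysis

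*Combined protocol and SAP*

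**What the plan says.** The two arm sections of the protocol describe the primary-endpoint test differently.

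- **Control** (Study Arm 2 procedures): "SVR12 laboratory testing will be performed by the community provider with at least one telephone reminder prior to lab due date". The same section adds regular research-assistant outreach, a requested release of information, and a visit link: "12 weeks post end of treatment study assessments will coincide with SVR12 lab results visit".
- **Telemedicine** (Study Arm 1 procedures): "SVR12 labs will be collected 12 weeks post-treatment in community partner labs", and "results will be relayed to the participant in the SVR12 follow up visit with the research assistant". Research assistants also take a dried blood spot at the SVR12 survey. The control section mentions no such specimen.

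Other text applies to everyone. The Phase 2 assessment table marks HCV RNA at 12 weeks post-treatment with a plain X, not the telemedicine-only mark. The SC Reviews Labs row is also marked at 12 weeks without restriction. Below the table: "Participants undergo phlebotomy at screening and 12 post end of treatment". The compensation table lists $40 for the 12-week draw with no arm limit. Study Measures plans on "Measuring detectable plasma HCV RNA for both participants who initiated and did not initiate within 6 months of randomization".

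Two rules decide how a result is scored. Under Data Analysis, Hypothesis 1, a missing viral load is non-suppressed in the main intention-to-treat analysis, with per-protocol and multiple-imputation sensitivity analyses. Under Study Measures: "Participants who did not start treatment within 6 months will be considered treatment failure".

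**The concern.** The primary outcome depends on a blood test, and the arms reach it differently in a trial that is not blinded. In the telemedicine arm it is tied to partner labs and a study visit. In the control arm it depends on an outside provider ordering it and on the result reaching the study.

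If a provider does not test, no text says that the study will draw blood instead. A release of information is requested, but no step is described for retrieving the RNA value. The stated purpose of chart abstraction is to count and classify peer interactions, and the items listed under it are the peer log and treatment-provider visits.

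Scoring missing as failure turns an ascertainment gap into an apparent treatment failure. At a given telemedicine capture, each cured control without a result moves the primary comparison toward telemedicine. The two sensitivity analyses could reveal this, but they do not replace the main result.

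**Working it through.** **Who can be affected.** Non-starters within 6 months fail whatever their RNA. Initiators who are not cured fail with or without a test. A missing test therefore changes the primary outcome only for cured initiators.

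**Is a back-up already written?** The compensation table has a $20 payment for a second draw after a missed one. It is listed directly after the screening draw, and Screening Procedures describes a second draw only for the screening confirmatory sample. It appears to belong to screening.

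**Inputs for the illustration.** The documents give no Phase 2 cure rate, capture rate, alpha, effect size or allocation ratio, so there is no plan figure to reproduce. Assumed: 1:1 allocation with 100 per arm (the protocol allows up to 200 in all), two-sided 0.05, and capture (share of cured participants with an RNA result on file) of 95% for telemedicine and 90%, 85% or 75% for controls. Rejection rates come from exact binomial enumeration of the pooled two-proportion z-test, standing in for the planned logistic regression.

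**Equal true cure.** Observed SVR = true cure × capture, so the spurious gap = cure × (0.95 − control capture). Example at 20% cure and 85% capture: 0.20 × 0.95 − 0.20 × 0.85 = 0.19 − 0.17 = 2 points.

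| True cure, both arms | Gap in points at 90 / 85 / 75% | Two-sided rejection at 90 / 85 / 75% | Rejection at equal 95% |
|---|---|---|---|
| 10% | 0.5 / 1 / 2 | 5.4 / 5.9 / 8.1% | 5.2% |
| 20% | 1 / 2 / 4 | 5.5 / 6.7 / 11.9% | 5.1% |
| 50% | 2.5 / 5 / 10 | 7.1 / 11.7 / 30.9% | 5.6% |

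**Unequal true cure.** Net bias = control cure × (1 − control capture) − telemedicine cure × 0.05. Break-even control capture = 1 − 0.05 × (telemedicine cure ÷ control cure).

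| Cure, telemedicine v control | Net bias in points at 90 / 85 / 75% | Break-even control capture |
|---|---|---|
| 60% v 20% | −1 / 0 / +2 | 1 − 0.05 × 3 = 85% |
| 60% v 40% | +1 / +3 / +7 | 1 − 0.05 × 1.5 = 92.5% |
| 50% v 40% | +1.5 / +3.5 / +7.5 | 1 − 0.05 × 1.25 = 93.75% |

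At 60% v 20% the chance of significance is about 100% at every capture level tried, so the inference does not change. At 50% v 40% it is 28.4% with equal 95% capture and 38.8 / 50.2 / 72.6% at control capture of 90 / 85 / 75%.

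**The case against.** The strongest reply is that the passages fit together: the schedule and payment table say that a 12-week draw happens, and the control section says who performs it. In neither arm is the phlebotomy assigned to study staff. Controls have outreach, a reminder, a coinciding visit and a requested release, and the unrestricted SC Reviews Labs mark implies that 12-week labs reach the study in both arms (SC is not expanded in the table). This stands as far as it goes and lowers the risk. It still supplies no back-up draw and does not name RNA as an abstracted result.

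The second reply concerns size. The documents' own pointers suggest that control cure may be low: the Background says fewer than 10% of people who use drugs access treatment, and the benefits section describes little treatment access in the region. These controls are insured, seeking treatment and helped by peers, so 10% is no forecast, but it belongs in the range, and there the effect is small.

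Some stronger readings are tempting, but the documents do not support them:

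- *Nobody is named for the control test.* The community provider is named.
- *The plan is silent on a missing test.* Data Analysis states how it is scored and adds sensitivity analyses. Only the operational fallback is absent.
- *The primary test has no upper time limit because of "which were collected on or after SVR12 timepoint".* Those words concern the use of survey data to classify participants with detectable RNA, which serves the relapse/reinfection endpoint. They do not set the primary window.
- *Non-initiators also need a back-up draw for the primary outcome.* They fail by definition.

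**Conclusion.** The point holds as a gap in how the primary endpoint is ascertained: the routes differ by arm, no back-up draw is written, retrieval of the RNA result is not spelled out, and a missing result is scored as failure. It should be fixed, because it bears on the primary comparison of an unblinded trial and most of the remedy is already listed in the protocol.

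A reader might infer that control capture will be lower, or that the main result will be biased toward telemedicine. The documents show neither. The size is unknown and every rate above is an assumption. With equal cure, the false-positive rate runs from 5.4% (10% cure, 90% control capture) to 30.9% (50% cure, 75% control capture), and the upper end needs both a high control cure rate and a 20-point capture gap. With a large true benefit, the net bias may be nil or against telemedicine. Confidence is medium.

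**What to change.** Reconcile the Arm 1 and Arm 2 SVR12 text with the assessment table and the compensation table by stating one ascertainment procedure for both arms:

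- the same window from end of treatment and the same reminders;
- a provider or chart RNA result accepted in either arm;
- a partner-lab draw arranged by the research assistant, using the 12-week test and $40 payment already listed, for any initiator with no in-window result.

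Name the RNA result as a chart-abstraction item, and report SVR12 capture by arm among initiators beside the primary result.

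The cost is protocol wording, one abstraction field, one results line, some research-assistant time and a few laboratory tests. The downside is slightly more post-treatment contact with controls.
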